Equipment used in this research meet all current safety standards, and all research staff will be highly trained in the use of all equipment. This study may include risks that are unknown at this time. Potential risks for this study are related to use of study product, neuroimaging, blood draw procedure, blood pressure measurement, the physical performance tests, the cognitive function tests, the sensory testing, and potential loss of confidentiality related to study participation, as discussed in detail below.

All assessment will be conducted at the Pain Clinical Research Unit (Dental Tower) and all sessions will be conducted by trained and certified research staff, which will monitor potential adverse experiences and symptoms. We will do safety labs within 48 hours if participant withdraws due to potential adverse effects to study drug (feeling weak/tired/low energy or changes in mental status). During the testing sessions, a fully equipped defibrillator is available along with a semi-automated ECG cart. All personnel associated with the study have received CPR training and training on management of acute events including syncope, chest pain, acute dyspnea, focal neurological symptoms and abnormal vital signs. Portable defibrillators are available at the assessment site. Additionally, a study physician is available on call and contact numbers for emergency services are posted. Institutional and community EMS services will be activated if needed. If participants develop chest pain, shortness of breath, or dizziness at any point during a screening or assessment visit, they will be instructed to rest and to contact the center and their physicians if these symptoms persist or recur.

Additionally, the study physician is available on call and contact numbers for emergency services are posted. Institutional and community EMS services will be activated if needed. If participants develop chest pain, shortness of breath, or dizziness at any point during a screening or assessment visit, they will be instructed to rest and to contact the center and their physicians if these symptoms persist or recur.

Participants will be instructed to talk with the investigators about any discomforts that occur during the study. If for any reason the participant reports an injury, chest pain, leg swelling or pain, excessive shortness of breath, abnormal heart rhythm or dizziness, they will be referred to their doctor, or the PIs will call the doctor or other health care provider.

Prior to beginning data collection, all study coordinators undergo standardized training on all study procedures. A detailed checklist for each data collection element is in place to ensure all study coordinators are appropriately trained and able to conduct study procedures. Research coordinators will be certified in each element of the study visit including obtaining informed consent, administering questionnaires, protecting confidentiality of collected data, performing the test batteries. Any study coordinator who is found to not adhere to all aspects of the protocol will be required to complete additional training followed by re-certification.

All research staff complete human subjects training required by The University of Florida institutional review board (IRB) and National Institutes of Health (NIH). This training includes education about the importance of maintaining confidentiality of personal health information. The study principal investigators or a co-investigator will be available to answer questions that arise during the informed consent process as needed. More information about specific protective measures against risk is outlined below.

Laboratory tests. Participants will have blood drawn at screening and during the post-intervention visit to measure their blood chemistry and will provide urine samples for osmolality tests. Abnormal results will be brought to the principal investigator's attention immediately. The results will be reviewed and signed by the study clinician and Drs. [name] and [name]. If a participant has both low sodium (<134mEq/L) and high osmolality (>1200L), we will conduct a second blood test. If the sodium is again low (<134mEq/L) in the repeat blood draw, the participant will be excluded.

Assessment of Adverse Events. A standard operating procedure will be established which is followed to collect and deal with adverse events during the research project. In particular, adverse events will be systematically monitored both during the sessions. In particular, participants will respond to a side effect check list to detect any possible physiological reactions related to the drug administration. This will include series of open-ended questions asked by trained research staff regarding any adverse events that have occurred since the last visit or phone contact. Open questions about pain experienced in various parts of the body will be delivered by study staff. Additionally, participants will be asked to the WOMAC and PANAS questionnaires to assess pain and feelings. This report will be reviewed by the principal investigator and study physician in a timely fashion. Any serious untoward event, whether related or unrelated to the study drug or procedures, will be reported to the UF IRB immediately as per their regulations.

Adverse events will be defined as any physical symptoms or side effects that began following session commencement. All reported and observed adverse events will be tracked in a running adverse events participant log, which will contain information regarding dates, description, and severity. All adverse events will be coded using the most current version of the Medical Dictionary for Regulatory

Activities (MedDRA). The number and percentage of participants reporting treatment-emergent adverse events will be tabulated by treatment, system organ class and MedDRA-preferred term. Treatment-emergent adverse events will be those adverse events that begin or worsened following the first dose of study drug. Adverse events will be further classified by severity and investigator-assigned relationship to the study variable. All reported and observed adverse events will be tracked on a running adverse events log (specific to each subject and maintained in his/her study file) and will contain information regarding onset/offset dates, time course (i.e., single, sporadic), severity, action taken regarding study drug, relationship to study drug, and whether it meets FDA criteria for "Serious." Each reported event is reviewed by the principal investigator and the study physician in a timely fashion. Additionally, the principal investigator reviews all adverse events recorded in each participant's log at the conclusion of study participation.

In Case of Emergency. Participants will have 24-hour access to emergency care and will be provided with a means of contacting the on-call study doctor and research staff. Participants will be informed and encouraged to contact the study physician and study staff immediately with medical concerns or unusual reactions. Participants will also be informed of the closest Emergency Department location to their residence.

Data and Safety Monitoring Plan. A Data Safety Monitoring Plan will be in place. In particular, the following procedures will be implemented to ensure data and participant safety. Study progress and safety will be reviewed by the principal investigators in collaboration with [name], M.D., the study MD, and [name], M.D., Ph.D., the sponsor of the IND and consultant on the project. The Independent Safety Monitor for this study will consist of an established senior investigator not associated with our study. A study end report will be compiled and will include a list and summary of adverse events. In addition, this report will address: (1) whether adverse event rates are consistent with pre-study assumptions; (2) reason for dropouts from the study; (3) whether all participants met entry criteria; (4) whether continuation of the study is justified on the basis that additional data are needed to accomplish the stated aims of the study; and (5) conditions whereby the study might be terminated prematurely. The annual report will be signed by the Independent Safety Monitor and will be forwarded to the IRB, NIH, and FDA. The Data Safety Monitoring Plan will also require that all significant serious adverse events that may be possibly related to the study participation will be reported to the IRB, FDA, and NIH within 48 hours of the principal investigators learning of the event. In addition, any unanticipated serious adverse events that may increase the risk of the research for participants or potential participants will be reported to the IRB and the NIH within 48 hours of the principal investigators being informed about the event. This study will be stopped prior to its completion if: (1) the intervention is associated with adverse effects that significantly impact the risk-benefit ratio, (2) study recruitment or retention becomes futile, (3) any new information becomes available during the trial that necessitates stopping the trial; or (4) if independent safety monitor indicates stopping trial is necessary due to adverse event frequency or severity.

ClinicalTrials.gov Requirements. In accordance with Public Law 110-85 and NIH guidelines, the proposed research will be registered with ClinicalTrials.gov prior to commencement of study procedures involving participants.

Blood Draw

The risks of drawing blood from a vein include discomfort at the site of puncture; possible bruising and swelling around the puncture site; rarely an infection; and, uncommonly, faintness from the procedure.

Blood Pressure Measurement

The risks of placing a blood pressure cuff on a participant's arms are that it may cause pinching or slight bruising.

Protocol: IRB201801467 (UCOPE Study)

IRB version: 10/1/2018

PI version: 05/10/2024

Physical Tests

There is a risk of losing balance and falling or development of chest discomfort due to coronary ischemia or dyspnea due to heart failure or lung disease associated with the physical performance-based testing (e.g., the ¼ mile walk test, balance tests, rising from a chair). We will minimize this risk by: (1) safely escorting participants to chairs located along the walking course should they become unsteady; (2) following participants at a close distance; and, (3) being at participants' side should they need assistance. Research staff members will be trained in the conduct of the physical performance tests before they work with study participants. Study staff members are trained not to perform these tests if they feel that testing is unsafe. In addition, participants will be asked whether they feel the test is safe. Those who state it may be unsafe will not be allowed to complete the test. Staff members will be trained to protect against falling and will be trained in CPR. They will be trained in activating the emergency response system at the research facility.

Sensory Testing

The sensory testing procedures may be uncomfortable or unpleasant, in that participants may experience some temporary discomfort from the thermal, pressure, and mechanical stimulation. However, if the participants feel the sensation is greater than they wish to tolerate, they can stop any of the procedures at any time.

Personal Information

Some of the questions participants will be asked may be personal in nature and may make participants feel uncomfortable. Time will be made to talk with the participant if they appear to be distressed. We will be asking for information about sensitive issues, such as mood and thoughts of suicide which may make participants feel uncomfortable. If they are uncomfortable answering these questions, they can choose not to answer and discontinue participation in the study. Some people, when asked such questions, experience strong emotional reactions that may require counseling. If they do, they are strongly encouraged to tell the Principal Investigator, who can make an appropriate referral to the Psychology Clinic or to the UF Counseling & Wellness Center at [contact]. If we find that the participant is suicidal, he/she will be excluded from further participation in the study and an appropriate referral will be made. If we should discover, based on the questionnaires or formal clinical interview, that the participant experiences marked depression or suffer from another psychiatric condition, we will offer to make an appropriate medical, psychiatric, and/or psychological referral.

Confidentiality

Data that will be collected from human subjects for this project will include behavioral performance measures, rating scales assessed through interviews and patients' responses to self-rated scales, physiological, and neuroimaging data. Data will be collected specifically for the proposed research project. Access to individually identifiable private information about human subjects will be limited to research staff affiliated with the project. Research records will be kept confidential to the extent provided by law. The collection and submission of medical information will be accomplished with strict adherence to professional standards of confidentiality. Participants' medical information will be kept in a secure location accessible only to research staff associated with this study. Participants will only be identifiable by ID number, and any published findings resulting from the study will not refer to or identify individuals. A number of methods will be employed to maintain confidentiality of participants. First, data will be collected in secure spaces where the session cannot be overheard. Secondly, only study investigators and key research staff (i.e. data manager and study programmers) will have access to the study database. Third, participants will be assigned a unique study identifier. Individual names are not linked with collected data in the password-protected study database and only the unique study identifier will

be used. A file linking the participant name and contact information and their specific study identifier will be kept separately and will be password protected and only accessible to study team members. Fourth, collected data will be maintained in locked computer files and file cabinets to which only study team members have access. Collected data will be used only for research purposes. Published data will not contain any individual identifiers. Finally, all research staff members have to retake refresher course certification exams every year.

Informed Consent

Prior to entry in the trial, the investigator(s) or study coordinator(s) will explain to potential participants the aims, methods, reasonably anticipated benefits, and potential hazards of the trial and any discomfort it may entail. Subjects will be informed that their participation in the study is entirely voluntary and that they may withdraw consent to participate at any time. They will be told that competent physicians/lab personnel will examine their records but that personal information will be treated as strictly confidential and will not be publicly available. Subjects will be given the opportunity to ask questions and will be given sufficient time to review all of the relevant information associated with the study. After this explanation and before entry to the trial, the subject's consent will be obtained and documented via signature of an informed consent form by both the subject and the person conducting the informed consent discussion. If signed informed consent cannot be obtained, the subject will not be included in the trial.

Inclusion of Women and Minorities/ Inclusion of Children

Men and women will be approximately equally represented in the sample. No clear evidence exists yet that OT levels vary between cultures. However, prosocial behavior associated with the OT system, have been shown to vary by culture (Kim et al., 2010). In addition, there is evidence that OT-related polymorphisms may vary across culture (Liu et al., 2010). Based on these empirically supported considerations we will enter race/ethnicity as covariate into our statistical models.

The proposed research will address effects of OT on pain, cognition, inflammation, and physical health in older men and women. Children are not the focus of this project, and by design, children will not be included in the study.

8. Possible Benefits

There are no direct benefits for study participation. There may be benefits that we are not yet aware of. The report about the results of the study will be made available to study participants as well as others in the community. However, the greatest benefit will be to society as a whole. Scientific knowledge advances slowly, but study results will increase our understanding of pain and cognition in aging. Such knowledge may be implemented in intervention programs that may have the potential to increase function and personal well-being.

9. Conflict of Interest

There are no conflicts of interest with this project.

References Cited (UCOPE):

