A notable characteristic of OT is that it is multifunctional in ways that may be leveraged therapeutically.¹⁴ OT's potential analgesic mechanisms may be explained by its roles as both a neurotransmitter and a paracrine hormone (**Figure 1**). As a neurotransmitter, OT may provide analgesia via widespread effects on the brain^{22,26} and spinal cord.²² As a hormone, OT is released into the peripheral circulation and acts directly on multiple organ systems. Possibly connecting these two routes, the OT-secreting system

Protocol: IRB201801467 (UCOPE Study)

IRB version: 10/1/2018

PI version: 05/10/2024

within the hypothalamus integrates neural, endocrine, and immune function.²⁶ Indeed, animal studies suggest that OT can inhibit inflammation both in the brain and spinal cord,²² with recent evidence supporting that OT's effect on inflammation may contribute to its analgesia. Similarly, in humans, OT decreases pro-inflammatory cytokines in the peripheral circulation,²³ and our preliminary data implicates both peripheral and central inflammatory processes in OT's analgesia.

Further, OT's effects in mood and affect regulation are likely explained by its interaction with the hypothalamic-pituitary-adrenal (**HPA**) axis and effects on stress regulation.^{26,49,50} Based on this combined evidence, our working hypothesis is that older adults with chronic knee OA may benefit therapeutically from OT's multiple pain-modulatory mechanisms.

5. Specific Aims

Specific Aim 1: To determine the effect of intranasal OT administration on clinical and experimental pain in older adults with symptomatic knee OA. We will assess self-reported pain along with a standardized, multimodal experimental pain battery, and plasma levels of OT as modifier of a significant treatment response. We will also assess physical, cognitive, and emotional functioning. Informed by our pilot data, we hypothesize that compared to P, OT treatment will result in significant reduction in: **H1a**) self-reported pain intensity; **H1b**) experimental pain sensitivity; and increase in **H1c**) physical, **H1d**) cognitive, and **H1e**) emotional functioning assessed with self-reported and performance-based measures.

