Pain and psychosocial questionnaires. We will also administer the West Haven Yale Multidimensional Pain Inventory providing well-validated measures of several important dimensions of the chronic pain experience. Multiple psychosocial factors have been related to chronic pain. We will assess psychosocial factors across the following broad domains. **1) Pain coping:** The Coping Strategies Questionnaire-Revised (**CSQ-R**)⁹⁴ consists of 27 items relating to how individuals cope with pain. It comprises six subscales based on pain coping strategies that individuals report (i.e., diverting attention, catastrophizing, praying and hoping, ignoring pain sensations, reinterpreting pain sensations, and coping self-statements). **2) Affective distress:** The Beck Depression Inventory, 2nd Edition⁹⁵ is a widely used depression scale that assesses affective (e.g., sadness, loss of interest), cognitive (e.g., worthlessness, guilty feelings), and somatic (e.g., changes in sleep, tiredness or fatigue) symptoms common amongst depressed individuals. It contains 21 self-report items assessing the frequency and severity of depressive symptoms over the previous two weeks.

Since item # 9 from the Beck Depression Inventory refers to suicidality, the experimenter will, before the end of the test session, review the participant's response to this item, and if the participant has chosen response option 2 = "I would like to kill myself" or 3 = "I would kill myself if I had the chance", the experimenter will contact the PIs immediately and the PIs or their designee will contact [name] (or her designee) at the University of Florida Psychology Clinic [contact]) who will make recommendations. In the unexpected event that the clinic personnel are not available, the Alachua County Crisis Center will be contacted. The same procedure will be implemented for the post-intervention assessment. The Positive and Negative Affect Scale (**PANAS**) is a 20-item scale that assesses positive and negative affect.⁹⁶ The PANAS has demonstrated adequate reliability and validity.⁹⁷ For this study, participants will be requested to provide "state" information by responding to items "at the present moment." **3) Satisfaction/quality of life:** We will assess self-reported quality of life using the 36-Item SF Survey Quality of Life⁹⁸ consistent with our pilot study, while the Satisfaction with Life Scale (**SWLS**)⁹⁹ will assess satisfaction with people's lives as a whole.

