We will compensate control participants with up to \$330 upon study completion in the form of a pre-paid, reloadable VISA card issued by the University of Florida or by cash payments. In particular, for completion of

- Screening Visit, Baseline Visit: \$75
- Sensory Visit: \$75
- Neuroimaging Visits (up to 2 visits): \$75 per visit
- (Optional) extra \$30 if you choose to participate in the nasal spray treatment.

Power and sample size considerations: Based on our pilot study estimates, we plan to recruit 160 participants, i.e., 80 participants in each of the randomly assigned treatment groups for the baseline visits. Assuming an attrition rate of 20% at the follow-up visits, we will have 128 participants (64 in the OT and 64 in the P group) at the 4-week post-intervention follow-up visits. This sample size yields a power over 0.80, even based on a very conservative Bonferroni correction for multiple comparisons (i.e., testing twelve hypotheses), which lowers the alpha level from $\alpha=0.05$ to $\alpha=0.006$. However, our proposed data-analytic strategy will use the Benjamini and Hochberg procedure to control for multiple comparisons, which is less stringent than the Bonferroni correction, and thus we expect the actual power to be larger than 0.80.

Hypotheses and data-analytic strategy: We summarize all hypotheses and planned analyses in **Table 3 for aims 1 and 2.** The statistical analyses will be conducted by Co-I [name] (Biostatistician) in

Protocol: IRB201801467 (UCOPE Study)

IRB version: 10/1/2018

PI version: 05/10/2024

collaboration with [name] (Consultant, Institute on Aging Biostatistics and Bioinformatics Core Leader, see letter of support) using R software. For studying the relationship between pre- to post-intervention (longitudinal) outcomes and predictors, we will fit linear mixed effects models (**LMEMs**) [1] with subject specific random effects to account for the within-subject correlation, by R function “lmer”.¹⁰⁹ Baseline outcomes and covariates will be adjusted to take account for confounding effects. Below is the formula for the linear mixed effect model:

$$y_{ik} = \mu + \alpha_i + \beta \mathbb{I}(z_i = 1) + \sum_{l=0}^L \gamma_l x_{il} + \eta \mathbb{I}(k = 2) + \theta \mathbb{I}(z_i = 1, k = 2) + \varepsilon_{ik}, \alpha_i \sim N(0, \sigma_0^2), \varepsilon_{ik} \sim N(0, \sigma^2) \quad [1]$$

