where y_{ik} is the outcome variable (e.g., pain intensity/sensitivity/function for Aim 1) for subject i and visit k ($k = 1$ for intervention and $k = 2$ for post-intervention); μ is the intercept term; $\alpha_i \sim N(0, \sigma_0^2)$ is the random effect with variance term σ_0^2 for subject i ; z_i is the treatment indicator with $z_i = 0$ for P and $z_i = 1$ for OT, β is the treatment effect (OT effect compared to P effect) and $\mathbb{I}(\cdot)$ is the indicator function which equals 1 if the argument inside (\cdot) is true and equals 0 otherwise; x_{il} is the l^{th} covariates for subject i with $l = 0$ for baseline level (e.g. baseline pain intensity before treatment for Aim 1) and $l = 1, 2, \dots, L$ for L covariates (i.e., age, sex, race...); η is the time effect of post-intervention visit compared to pre-intervention visit; θ is the interaction effect between post-intervention and OT; $\varepsilon_{ik} \sim N(0, \sigma^2)$ is the error term with variance σ^2 . From equation [1], we will test whether there is a significant OT effect for both intervention and post-intervention. LMEMs allow for missing data if missing-at-random (MAR).

Table 3. Proposed hypotheses and planned analyses.

Specific Aims	Hypotheses	Planned Analyses
#1: Clinical and experimental pain	H1a: OT vs. P administration will reduce self-reported pain intensity	LMEMs* ; DV: Clinical pain IV: Treatment (OT/P)
	H1b: OT vs. P administration will decrease experimental pain sensitivity	LMEMs* ; DV: QST IV: Treatment (OT/P)
	H1c-1e: OT vs. P administration will increase physical, cognitive and emotional function	LMEMs* ; DV: SPPB, Exe. Function, Catastrophizing IV: Treatment (OT/P)
#2: Inflammatory mechanisms	H2a: OT vs. P will decrease systemic inflammation	LMEMs* ; DV: Plasma cytokines (IL6, TNF α , IL10) IV: Treatment (OT/P)
	H2b: OT vs. P will decrease brain metabolite concentrations associated with neuroinflammation	LMEMs* ; DV: Brain metabolites (tCr, MI, Cho) IV: Treatment (OT/P)
	H2c: Decrease in brain metabolites and systemic cytokines will be associated with decrease in clinical pain	Correlations/ Regressions IV: Decrease in brain metabolites and systemic cytokines DV: Decrease in clinical pain

Note. **IV** = Independent variable; **DV** = Dependent variable; **LMEMs**: linear mixed effects models; *Adjusted for baseline outcomes and covariates (age, sex, race, BMI, KL score, hip OA, plasma biomarkers).

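### H1e predicts better emotional functioning, but the only outcome named for it is catastrophizing, a pain-coping subscale, and no affect measure is named in any planned test

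*Combined protocol and SAP*

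**What the plan says.** Section 5, Specific Aim 1, states H1c to H1e together: oxytocin, compared with placebo, will increase physical, cognitive and "emotional functioning assessed with self-reported and performance-based measures".

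Section 6, Hypotheses and data-analytic strategy, introduces Table 3 with the words "We summarize all hypotheses and planned analyses in" that table, for Aims 1 and 2. The row for H1c-1e sets physical, cognitive and emotional function against "DV: SPPB, Exe. Function, Catastrophizing", with treatment as the independent variable.

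Section 6, Pain and psychosocial questionnaires, sorts the instruments into domains. Domain 1 is pain coping and holds the CSQ-R: "It comprises six subscales based on pain coping strategies that individuals report (i.e., diverting attention, catastrophizing, praying and hoping" and three others. Domain 2 is affective distress and holds the BDI-II, which "is a widely used depression scale that assesses affective", cognitive and somatic symptoms, and the PANAS, which "is a 20-item scale that assesses positive and negative affect". The SF-36 is in domain 3, on satisfaction and quality of life.

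The text after Table 3 makes emotional functioning measures secondary outcomes of Aim 1, without naming an instrument, and applies equation [1] to H1a through H1e.

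**The concern.** The Background supports H1e with findings on mood and affect. It says acute oxytocin improves mood and positive affect in younger people, and it attributes oxytocin's role in mood and affect regulation to the HPA axis and stress regulation. The Abstract reports a pilot gain in self-reported emotional functioning. The one outcome named for H1e is instead a subscale about how people respond to pain.

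Such a score can fall because pain falls. If it does, the report could say that oxytocin improved emotional functioning when the evidence concerns pain coping only. An effect on mood that did not run through pain might never be formally tested, because no instrument is committed to it. If instead the unnamed secondary measures are meant to include the affect scales, the choice among them is open until the data are seen.

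**Working it through.** **1. Which outcome belongs to H1e.** The Table 3 row has three hypotheses and three dependent variables. SPPB is physical (H1c) and executive function is cognitive (H1d), so catastrophizing is left for H1e. The CSQ-R is the only instrument described as yielding it.

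**2. Where the affect instruments appear in the analysis.** BDI-II, PANAS and SF-36 are named neither in Table 3 nor in the analysis text that follows it.

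**3. Whether the model separates emotion from pain.** The Table 3 footnote lists baseline outcome, age, sex, race, BMI, KL score, hip OA and plasma biomarkers. It has no term for change in pain, and no mediation analysis is planned for H1e. Equation [1] therefore estimates a total effect.

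**4. How many tests the plan counts.** Power and sample size considerations refers to twelve hypotheses. One reading of Table 3 gives that number: H1a 1 + H1b 1 + H1c-e 3 + H2a 3 + H2b 3 + H2c 1 = 12. This leaves one test for H1e and none for BDI-II or PANAS. The stated Bonferroni alpha of 0.006 does not reproduce, because 0.05/12 = 0.0042. That is a separate error and does not affect this point.

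**5. Cost of adding affect outcomes.** Inputs from the plan: 160 × (1 − 0.20) = 128 completers, 64 per group. For a two-sided test with 80% power, the detectable standardised effect is √(2/64) × (z₁₋α/₂ + 0.842), with √(2/64) = 0.1768.

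| Tests | Bonferroni α | z₁₋α/₂ | Detectable d |
|---|---|---|---|
| 12 (as counted) | 0.00417 | 2.865 | 0.655 |
| 13 (add BDI-II) | 0.00385 | 2.891 | 0.660 |
| 15 (add BDI-II and both PANAS scales) | 0.00333 | 2.935 | 0.668 |

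The increase with three added tests is 0.668 − 0.655 = 0.013 SD.

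**6. Could lower pain alone move the H1e outcome?** The documents give no effect size and no correlation between pain and catastrophizing, so this step is illustrative. Assume that oxytocin lowers pain by d = 0.644 (the effect with 80% power at 64 per group and α = 0.006, by noncentral t), that a share of 0.4 to 0.6 carries over to catastrophizing, and that affect does not change. Catastrophizing then falls by 0.4 × 0.644 = 0.26 to 0.6 × 0.644 = 0.39 SD. The chance of a significant H1e result is:

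| Analysis | α = 0.05 | α = 0.006 |
|---|---|---|
| 64 vs 64 | 0.30 to 0.58 | 0.10 to 0.28 |
| 128 paired, within-person r = 0.5 | 0.83 to 0.99 | 0.55 to 0.94 |

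At r = 0.5 the paired effect is d/√(2(1 − 0.5)) = d. The plan uses Benjamini-Hochberg, so the working threshold would usually lie between the two columns. The spread from 0.10 to 0.99 shows that the mechanism is possible. It does not estimate how likely it is.

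**The case against.** A reader might infer that the affect measures have no planned test at all. The documents do not support that. The text after Table 3 makes emotional functioning measures, in the plural, secondary outcomes and applies equation [1] to H1a through H1e, which can be read to include BDI-II and PANAS. Nor is Table 3 complete: H2d is missing, and entries such as clinical pain and QST are shorthand for several measures. What stands is narrower: no affect instrument is named for any test, and catastrophizing is the only named H1e outcome.

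The domain headings organise questionnaires and do not assign them to hypotheses. For controls, the protocol describes the same questionnaire set as capturing daily pain and emotional functioning, and Table 3 itself treats catastrophizing as emotional. Whether it is a valid emotional outcome is a judgement of construct that the documents do not settle. They do separate it from affective distress.

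Another tempting reading is that a switch to BDI-II would remove the influence of pain. It would not. Lower pain can also lower BDI-II, which includes sleep and fatigue items, and H1e does not claim an effect independent of pain.

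Finally, replacing a listed outcome in a trial that the ancillary PANDA protocol describes as ongoing would invite a charge of outcome switching. That objection stands, and it favours adding an outcome over substituting one.

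**Conclusion.** The point holds as a gap in outcome specification for a secondary hypothesis. As written, H1e can be declared supported on a pain-related coping score without evidence on mood or affect, which is what the Background offers as its rationale. This rests on the text alone and does not depend on the illustration in step 6.

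The size of the risk cannot be computed from the documents, because the effect on pain, the carry-over and the within-person correlation are all unstated. The gap does not make H1e invalid and does not touch the primary outcome of Aim 1. It limits what a positive H1e result may be said to show.

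**What to change.** Before unblinding, and with a dated justification:

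- Add BDI-II total to the H1e row of Table 3, with PANAS as support. Both are already collected at the pre and post sensory visits. The two-week recall of BDI-II fits inside each four-week phase, whereas PANAS is asked about the present moment.
- Keep catastrophizing in the row, labelled as a pain-coping outcome.
- State the direction of benefit for each score.
- Count the added tests in the Benjamini-Hochberg family.
- State that any claim about emotional functioning rests on the affect measure and is a total effect, not one independent of pain.

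The alternative is to restate H1e as a hypothesis about pain catastrophizing.

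The cost is one to three more tests, with the detectable effect rising from about 0.655 to at most 0.668 SD under Bonferroni. No new instrument is needed. BDI-II could be missing more often than CSQ-R, because the Research Plan keeps questionnaires with suicidality items in person while other parts may be done remotely or dropped. Completeness should be reported for both.
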